- During the CRT treatment period, subjects will be assessed twice weekly for the presence and severity of OM by trained evaluators using the WHO grading scale for OM. Subjects will complete a daily study diary (including weekend days). The diary contains Question 2 of the Oral Mucositis Daily Questionnaire (OMDQ), a record of daily analgesic use for mouth and/or throat pain, a record of the study drug oral rinses performed each day, and the subject's assessment of mouth sensations. The diary will be reviewed by a member of the study staff each day during the first week (at least 5 days) of study treatment to ensure that the subject is appropriately completing the diary. If subject diary completion is satisfactory, then the diary will be reviewed at least once weekly during the remainder of the study. At weekly intervals (on the same day of each week), subjects will complete the FACT-H&N instrument to record quality of life responses.
- Single samples (venous blood) for assessment of brilacidin plasma concentrations will be obtained from each subject at weekly intervals during the CRT treatment period. These blood samples may be obtained at the time of the venipuncture for clinical laboratory tests as specified by the protocol.
- For those subjects who have consented to gene analysis, samples of venous blood will be obtained at baseline, during week 3, and on the last day of radiation.
- All subjects will be evaluated at 1 week after RT completion (or withdrawal from the study) for assessment of the presence and severity of OM and other safety assessments. Subjects having an WHO OM Grade ≥ 2 at this post-treatment visit will return to the clinic at weekly intervals until mucositis resolves to WHO OM Grade < 2 ; subjects having a WHO OM Grade ≤ 1 may be followed by weekly phone call instead. During the post-RT period, subjects will continue to complete the daily study diary

that contains Question 2 of the OMDQ as well as recording analgesic use and subjects will complete the FACT-H&N QOL instrument weekly until 4 weeks (\pm 2 days) post-RT. In most instances the last study related visit, the End of Study (EOS) visit, will be at Week 4 post-RT.

Patient Eligibility:

- Patients with recently diagnosed (within previous 6 months), pathologically-confirmed, non-metastatic squamous cell carcinoma of the oral cavity, oropharynx, hypopharynx, or supraglottic larynx.

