Brilacidin (45 mg/ 15mL WFI) oral rinse tid, or placebo (15mL WFI) oral rinse tid

Efficacy and Safety Endpoints:

Primary Efficacy Endpoint

Incidence of severe OM (WHO Grade ≥ 3) experienced during radiation therapy by subjects with HNC receiving concomitant chemoradiation therapy and a cumulative radiation dose of at least 55 Gy.

Secondary Efficacy Endpoints

- Duration of severe OM (WHO Grade ≥ 3), from initial WHO Grade ≥ 3 during radiation therapy to the first WHO Grade 2 or lower OM assessment during/after radiation therapy.
- Duration of severe OM (WHO Grade ≥ 3), from initial WHO Grade ≥ 3 during radiation therapy to the last WHO Grade ≥ 3 assessment during/after radiation therapy.
- Time to onset of severe OM (WHO Grade ≥ 3).
- Incidence of severe OM (WHO Grade ≥ 3) by cumulative IMRT.

Safety Endpoints

The safety and tolerability of treatment with brilacidin will be assessed through incidence, severity and type of adverse events, including serious adverse events, and changes in clinical laboratory parameters, blood pressure, heart rate, ECOG, and body weight.

Systemic Exposure/Pharmacokinetic Endpoints

Brilacidin systemic exposure will be estimated from plasma sample concentrations; samples will be obtained from each randomized subject at weekly intervals during the CRT treatment period.

Data Analysis:

Efficacy Analyses

Full details of the statistical methodology for summary and analyses of the data collected in this study will be prepared separately from this protocol in a Statistical Analysis Plan (SAP).

The primary efficacy objective is to evaluate brilacidin compared to placebo in reducing the incidence of severe OM (defined as grade 3 or 4 on the WHO Oral Mucositis scale, WHO Grade ≥ 3) in subjects with HNC receiving concomitant chemoradiation therapy and a cumulative radiation dose of at least 55 Gy. For this comparison the Fishers Exact Test will be used.

Time to onset of severe OM (WHO Grade ≥ 3) will be assessed using the log rank test. Both a scale of days, and a scale of cumulative radiation dose delivered (Gy) will be used for the

Kaplan-Meier analysis. The log rank test will be used to compare treatment groups at time of onset of severe OM. Time to onset of ulcerative OM (WHO Grade ≥ 2) will be explored similarly.

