Duration of severe OM (WHO Grade ≥ 3) is evaluated two different ways: (1) Initial instance duration of severe OM is defined as the number of days from initial WHO Grade ≥ 3 during radiation therapy until the first WHO Grade 2 or lower OM Grade occurs; (2) Overall duration of severe OM is defined as the number of days from initial WHO Grade ≥ 3 during radiation therapy to the last WHO Grade ≥ 3 assessment during/after radiation therapy. If any subject does not experience severe OM, his/her duration will be set to 0. Subjects who experience severe OM but do not resolve to WHO Grade 2 or lower will be censored at the last study visit. The effect of treatment on the duration of severe OM will be assessed using a log rank statistic. Analyses will be done using both a scale of days, and a scale of cumulative radiation dose delivered (Gy).

Safety Analysis

All safety data, demographic and baseline characteristics will be summarized descriptively through appropriate data tabulations, descriptive statistics, and categorical summaries.

Changes in blood pressure, heart rate, and hematology and clinical chemistry parameters from baseline to the end of the study will be summarized. Treatment-emergent changes from values within normal range to abnormal values in clinical laboratory parameters will be identified by means of summary and shift tables. ECOG and body weight changes from baseline to the end of the study will also be summarized.

Interim Analysis

Ad-hoc interim analyses may be conducted to support decision making concerning the current clinical study, the Sponsor's clinical development projects in general or in case of any safety concerns. Such analyses may be unblinded, and the details will be documented in the SAP.

Sample Size

The proportion of subjects experiencing severe OM (WHO Grade ≥ 3) after a total cumulative radiation dose of at least 55 Gy (and no more than 72 Gy) is unknown but expected to be approximately 75% for the placebo oral rinse treatment group, and the assumption for the active Brilacidin oral rinse treatment group is estimated to reduce to approximately 35-40%. Based on these assumptions, a sample size of 23-30 subjects per treatment group is appropriate to detect the specified difference with at least 80% power.

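### Duration of severe OM is set to 0 for subjects who leave before severe OM could appear, so unequal early withdrawal biases both secondary duration endpoints

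*Combined protocol and SAP*

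**What the plan says.** The Efficacy Analyses part of the protocol synopsis introduces the endpoint with "Duration of severe OM (WHO Grade ≥ 3) is evaluated two different ways": the first severe episode until Grade 2 or lower, and the span from the first to the last severe grade. Both start from a severe grade recorded during RT. Three sentences then govern both versions:

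- Subjects never severe: "If any subject does not experience severe OM, his/her duration will be set to 0".
- Censoring: "Subjects who experience severe OM but do not resolve to WHO Grade 2 or lower will be censored at the last study visit".
- Test: "The effect of treatment on the duration of severe OM will be assessed using a log rank statistic", on a scale of days and on a scale of cumulative Gy.

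Withdrawal is mentioned under Design and Methodology, where the post-treatment visit rule begins "All subjects will be evaluated at 1 week after RT completion (or withdrawal from the study". The primary incidence endpoint is tied to "concomitant chemoradiation therapy and a cumulative radiation dose of at least 55 Gy"; the duration endpoints carry no such condition. Full statistical detail is deferred to a separate SAP. The text available for this review gives no dropout rate and no rule for withdrawals in the duration analysis.

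**The concern.** The zero rule covers two different kinds of subject. One was graded to the end of RT and never became severe, so a duration of 0 is a fact. The other left in, say, week 2 with no severe grade on record, so whether severe OM would have followed is unknown. Both receive 0, the most favourable value on the scale. The only censoring rule requires that severe OM has already occurred, so it cannot reach the second subject.

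Early departure is thus scored as success. If brilacidin loses more subjects early, the drug appears to shorten severe OM. If placebo loses more, a real benefit is diluted.

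**Working it through.** **Inputs from the documents.** Placebo incidence is "expected to be approximately 75% for the placebo oral rinse treatment group"; the brilacidin rate is "estimated to reduce to approximately 35-40" per cent. The plan is 23-30 subjects per arm, about 60 in all, randomized 1:1, with OM graded twice weekly during chemoradiation (a 3.5-day grid).

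**The plan's own figure.** The only stated size is for the primary endpoint. With n = [1.96·√(2p̄q̄) + 0.842·√(p₁q₁ + p₂q₂)]² / (p₁ − p₂)²:

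- 75% v 35%: (1.379 + 0.542)² / 0.16 = 23.1
- 75% v 40%: (1.370 + 0.550)² / 0.1225 = 30.1

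This agrees with 23-30 apart from rounding up (24 and 31). It confirms the incidence inputs but says nothing about duration.

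**Assumed, because the documents are silent.** Alpha is two-sided 5%. Severe episodes follow a gamma distribution with mean about 20 days, on the 3.5-day grid, censored at 60 days. Early leavers go before onset and independently of OM risk. A duration of 0 counts as an event at time 0. There are 30 subjects per arm and 4,000 simulated trials per scenario; Monte Carlo error is about √(0.10 × 0.90 / 4000) = 0.5 points near 10%.

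**Share of zeros under the rule.** With early-withdrawal proportion d and incidence p, the share scored 0 is d + (1 − d)(1 − p). When p is equal in the two arms, the spurious gap is p × (difference in d). With p = 75% in both arms:

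| Leaving early, placebo v brilacidin | Share scored 0 | Spurious gap | False-positive rate under the rule |
|---|---|---|---|
| 10% v 10% | 32.5% v 32.5% | 0 | about 5-6% |
| 10% v 20% | 32.5% v 40.0% | 7.5 points | about 7% |
| 10% v 25% | 32.5% v 43.75% | 11.25 points | about 9-10% |
| 10% v 30% | 32.5% v 47.5% | 15 points | about 11-12% |

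The excess falls almost wholly on one side. In one run at 10% v 30%, the error was 11.9%, of which 11.4 points favoured brilacidin, against a nominal 2.5. Leaving early leavers out returns the total to about 5-6%, split roughly evenly.

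**When brilacidin works (75% v 40%).** Chance of a significant log rank result; without withdrawal it is about 42%:

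| Leaving early, placebo v brilacidin | Rule as written | Leavers left out | Leavers censored at time 0 |
|---|---|---|---|
| 25% v 10% | about 19% | about 34% | about 45% |
| 10% v 25% | about 50% | about 36% | about 23% |

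The last column shows why censoring at time 0 is no remedy. Subjects censored at 0 stay in the risk set at time 0, where the true zeros are events, and so count as people who did not have a zero duration. The bias then runs the other way. With no treatment effect and 10% v 25% leaving, the total error is a reassuring 5.4%, but it splits 1.4% for brilacidin and 4.0% for placebo.

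**Different assumptions.** With exponential episodes (mean 20 days), censoring at day 77 and 5% v 25% leaving, the null error was 13.0% under the rule and 5.1% with leavers left out. Mean duration was 13.8 v 10.8 days, a difference of 3.0 days with no true effect.

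**The case against.** **The harm needs an imbalance that the documents do not predict.** This stands. The trial is double-blind, the endpoints are secondary, and with equal withdrawal the rule does little. At 10% v 15% the null error was only 5.9%. On the other hand, in an arm of 30 a 15-point gap is 0.15 × 30 = 4.5 subjects, which is not a remote possibility.

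**Withdrawal is only mentioned.** Also right. A reader might infer that the plan expects many early leavers, or that brilacidin will lose more because of the rinsing burden. The documents support neither. Withdrawal appears in a parenthesis, exclusion criterion 20 screens out those unwilling to rinse, and nothing says that stopping the rinse ends OM grading. Weekly return visits for subjects at Grade 2 or above after treatment also narrow the gap, though not for someone who leaves at Grade 0 or 1.

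**The 55 Gy condition may remove early leavers.** It would remove most of them if it defined the duration analysis set, but the text attaches it to the primary endpoint. It would also be an exclusion made after randomization.

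**The separate SAP may settle it.** Possibly. But the synopsis does not leave this open: it states a rule, and an SAP that followed it would carry the problem forward.

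**Nothing says in words that a zero is a completed event.** True; this is inferred. The text assigns a value and reserves censoring for other subjects, so it is the natural reading.

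**Conclusion.** The point holds as a defect in a stated rule. Followed literally, the text gives early leavers the best outcome on both duration endpoints and on both scales. The direction cannot be known in advance, so the plan cannot be said to favour brilacidin. The effect is negligible with balanced withdrawal, modest at a 10-point gap (about 7% error) and material at 15-20 points (about 9-12%). Where the drug works, a 15-point gap moves the chance of significance from about 34% down to 19%, or from about 36% up to 50%, depending on which arm loses more. These sizes rest on assumed withdrawal rates, episode lengths and alpha, and on withdrawal unrelated to OM risk. The calculations concern duration only and support no inference about the primary endpoint. The wording should be corrected before unblinding.

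**What to change.** Replace the zero-duration sentence with:

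> Duration is set to 0 only for subjects graded through the end of RT with no WHO Grade ≥3. Subjects whose OM assessments stop earlier with no Grade ≥3 have missing duration and are left out of the main log rank comparison; their number is reported by arm, and a worst-case sensitivity analysis is run.

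The end of RT is the natural cut-off because both definitions count only episodes that start during RT. The SAP should say how the worst case is built, for example brilacidin leavers given the longest observed duration and placebo leavers 0. It should also rule out coding leavers as censored at time 0 while true zeros are events there.

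The cost is a short replacement text and one sensitivity run. Slightly fewer subjects enter the duration test. Leaving subjects out after randomization is unbiased only if leaving is unrelated to OM risk, which is why the counts by arm and the sensitivity analysis are needed.

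### One censoring rule serves two duration endpoints but fits only the first: a subject who dips, relapses and is still severe when last graded gets a completed overall duration

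*Combined protocol and SAP*

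**What the plan says.** All of this is in the protocol synopsis. Under Data Analysis, Efficacy Analyses, the text opens with "Duration of severe OM (WHO Grade ≥ 3) is evaluated two different ways". The initial-instance duration starts at the first severe grade and runs "until the first WHO Grade 2 or lower OM Grade occurs". The second measure is worded "Overall duration of severe OM is defined as the number of days from initial WHO Grade ≥ 3 during radiation therapy" and runs to the last severe grading, whether that falls in or after radiotherapy. It therefore spans any dip below Grade 3. The list of Secondary Efficacy Endpoints carries both measures, without a censoring rule for either.

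One censoring sentence follows the two definitions: "Subjects who experience severe OM but do not resolve to WHO Grade 2 or lower will be censored at the last study visit". The analysis is the same for both: "The effect of treatment on the duration of severe OM will be assessed using a log rank statistic".

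The assessment schedule is under Design and Methodology. During chemoradiation "subjects will be assessed twice weekly for the presence and severity of OM by trained evaluators". Everyone is evaluated again one week after radiotherapy ends or after withdrawal. Those at Grade 2 or above at that visit "will return to the clinic at weekly intervals until mucositis resolves to WHO OM Grade < 2". The last visit is in most cases at Week 4 after radiotherapy.

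**The concern.** A log rank test uses two items per subject: a time and an indicator of whether the episode was seen to end. The censoring sentence sets that indicator by whether severe OM came down to Grade 2 or lower. That is exactly what ends the initial-instance duration. It is not what ends the overall duration, which continues through a dip.

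The subject at issue is severe, has at least one reading of Grade 2 or lower, becomes severe again, and is severe at the last grading. With two gradings a week this pattern can be recorded, and there would be little reason to define two durations unless relapse was expected. On the plain reading this subject has resolved and is not censored. The overall duration is then analysed as finished on the day observation stopped.

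At stake is the accuracy of the Kaplan-Meier curve and the log rank result for overall duration. If the point stays open, someone must choose between the two readings when the analysis is programmed.

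**Working it through.** The plan gives no figure for either duration, so there is none to reproduce. The check is to apply the definitions and the censoring sentence to short grade sequences.

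**Inputs.** Definitions and rule as cited above. The days are illustrative: gradings on Days 30, 34 and 38, last seen on Day 38.

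**Formulas.**
- Initial-instance time = day of first Grade 2 or lower after onset − day of onset.
- Overall time = day of last Grade 3 or higher − day of onset.
- Reading A: censor if no Grade 2 or lower was recorded after onset.
- Reading B: censor if the subject is not at Grade 2 or lower when last seen.
- A censored time runs to Day 38.

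**Results** (days, status).

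| Grades | A: initial | A: overall | B: initial | B: overall |
|---|---|---|---|---|
| 3, 2, 3 | 4, event | 8, event | 8, censored | 8, censored |
| 3, 3, 3 | 8, censored | 8, censored | 8, censored | 8, censored |
| 3, 3, 2 | 8, event | 4, event | 8, event | 4, event |
| 3, 2, 2 | 4, event | 0, event | 4, event | 0, event |

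The readings differ only in the first row. Under A the initial-instance result is right (34 − 30 = 4, end observed), but the overall duration (38 − 30 = 8) is called complete while the subject is severe. Under B the overall duration is properly censored, but the initial-instance duration becomes 8 days censored although its end was seen on Day 34. No single reading serves both definitions.

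The overall time is 8 days under either reading. Only the indicator changes. Coded as an event with n subjects at risk, this subject multiplies the Kaplan-Meier estimate by (1 − 1/n) and adds one event to the log rank. Coded as censored, the subject does neither.

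**How many subjects.** The documents give no duration, dip rate or share still severe at the end, so the following rests on assumptions. The expected number of severe cases, with 30 per arm and the synopsis rates of 75% and 40%, is 30 × 0.75 + 30 × 0.40 = 34.5, or about 34. Simulations assumed Weibull durations (shape 1.5), a 10–20% chance per grading of a transient Grade 2, and gradings twice weekly in radiotherapy, then weekly to Day 75 (about Week 4 after radiotherapy). Miscoded subjects = severe cases × share still severe at the end × share of those with an earlier dip:

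- Mean 21 days: 34 × 0.09 × 0.42 = 1.3 (10% dips) to 34 × 0.08 × 0.67 = 1.8 (20% dips).
- Mean 28 days: 34 × 0.19 × 0.44 = 2.8 to 34 × 0.17 × 0.69 = 4.0.
- Mean 14 days: below 0.5.

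Varying the assumed onset window gave 0.9–3.4 over similar settings. Letting weekly visits for unresolved cases run to Day 105 gave 0.1–0.6, with 0.3–2.5% of severe cases still unresolved. In the same runs, significance at 0.05 changed in 1.6–6.4% of trials with the Week 4 stop and in 0–1.4% with the longer follow-up.

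**The case against.** The strongest reply is that the sentence does not say *ever*. A subject back at Grade 3 at the last visit can fairly be said not to have resolved, and a programmer could apply the sentence to each duration on its own terms. The synopsis also defers full statistical detail to a separate SAP, where event and censor flags normally belong.

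Part of this stands: a sensible programmer might well reach the right coding. But that means giving one sentence two meanings, which the text does not invite. The deferral does not cure a rule that the protocol already states, and nothing in the supplied text settles the point.

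The reply has more force on consequences. A reader might infer any of the following, and the documents do not support them:

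- *That recorded durations are too short.* The days are the same either way. Only the Kaplan-Meier estimate and the log rank move.
- *That subjects who leave while severe are generally coded as recovered.* Uninterrupted severe OM is censored under either reading. Only those with an earlier dip are affected, and the plan schedules a further OM evaluation one week after withdrawal, which may change the last grade.
- *That the treatment comparison is biased.* This would need dips, relapse or withdrawal to differ by arm. The documents give no rates, and no such difference has been shown.
- *That several subjects are certain to be miscoded.* The upper figures need a fixed stop at Week 4. Design and Methodology names Week 4 as the end-of-study visit, but calls it the last visit only in most instances and ties weekly visits to resolution, so a fixed stop is not clearly imposed.
- *That a reported share resolved is wrong.* The listed endpoints include no such measure.

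**Conclusion.** Wrong as written, minor severity. The rule suits the initial-instance duration and miscodes the overall duration for subjects who relapsed and were severe at their last grading; the alternative reading moves the error to the other endpoint. This conclusion follows from the text alone and needs no assumption.

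The size does rest on assumptions: from under 1 to about 4 subjects per trial, depending on mean duration, dip rate and whether unresolved cases are followed past Week 4. The effect is confined to the event indicator of one secondary endpoint and is probably small. Neither the size nor the direction of any bias between arms can be computed from the documents. The primary endpoint and the 23–30 subjects per group are unaffected.

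**What to change.** Split the sentence in the protocol and carry both parts into the SAP:

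- **Initial-instance duration:** keep the present rule, censoring only when no grade of 2 or lower is recorded after onset.
- **Overall duration:** treat the episode as ended only if the subject's last WHO assessment is Grade 2 or lower. If it is Grade 3 or higher, censor at that assessment, whatever dips came earlier.

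The cost is a sentence or two, with no new data and no extra visits. It should be done before unblinding, so that the choice between readings is not made with results in view.

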- To evaluate the efficacy of topically applied brilacidin in reducing the duration of severe OM (WHO Grade ≥ 3) in subjects with HNC receiving concomitant chemoradiation therapy.
- To evaluate the efficacy of topically applied brilacidin in delaying the onset of severe OM (WHO Grade ≥ 3) in subjects with HNC receiving concomitant chemoradiation therapy.

Design and Methodology:

The study is a Phase 2, randomized (1:1 ratio), double-blind, placebo-controlled, 2-arm trial to be conducted in patients receiving chemoradiation for the treatment of squamous cell carcinoma of the oral cavity, oropharynx, hypopharynx, or supraglottic larynx.

Patients with this diagnosis whose anticipated treatment includes chemoradiation therapy (CRT) and who consent to participate will enter a screening period of up to 45 days prior to the anticipated initiation of CRT. If eligible, subjects will be randomized to one of the two blinded study treatments and will enter the treatment phase of the study (approximately 11 weeks in duration).

For entry into the study, eligible patients will have recently-diagnosed (in the previous 6 months), pathologically-confirmed, non-metastatic squamous cell carcinoma of the oral cavity, oropharynx, hypopharynx, or supraglottic larynx. Tumor staging for eligibility, using AJCC Tumor Staging Guidelines, or as determined by institutional tumor board review may be determined from scans (CT, PET, and/or MRI) obtained within 120 days prior to consent for screening. Scan interpretation should follow Response Evaluation Criteria in Solid Tumors (RECIST) Version 1.1 criteria (Appendix E).

Patients must be scheduled to receive a continuous course of intensity-modulated radiation therapy (IMRT) with a minimum cumulative dose of 55 Gray (Gy) and maximum cumulative dose of 72 Gy over approximately 7 weeks (treatment week is defined as a 7-day period, irrespective of the day of the week that the 7-day period begins). Planned radiation treatment fields must include at least two oral sites (buccal mucosa, floor of mouth, ventral/lateral tongue, soft palate). The treatment plan must include chemotherapy with cisplatin administered in standard weekly (30-40 mg/m²) or approximately every 21 days (80-100 mg/m²) regimens. No other chemotherapy is allowed during radiotherapy unless intolerance to cisplatin is demonstrated during study participation. In this case, with medical monitor approval, carboplatin may be substituted.

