Eligible subjects will be randomized to receive one of the following study drug regimens during participation in the study (1:1 ratio):

Arm A: Placebo (WFI) [oral rinse tid]

Arm B: Brilacidin 3 mg/mL in WFI [oral rinse tid]

The study drug will be administered as an oral rinse three times daily (approximately 6 hours between oral rinses) beginning on the first day of radiotherapy and continuing each day (including weekends) until the completion of the course of chemoradiation. The

subject will be instructed to use the study oral rinse three times each day with approximately 6 hours between each use, whenever possible. Subjects will be instructed to perform the oral rinse for 1-minute and *spit out the rinse after each use, avoiding swallowing any of the rinse*. The first use of oral rinse on the first day of study drug treatment must be witnessed by a member of the study staff. Subjects will be told not to eat, brush their teeth, chew gum, or suck on hard candy, cough drops, etc., for at least 10 minutes before each oral rinse. A subject should rinse his/her mouth with plain water prior to administering the oral rinse. Subjects will be told not to eat, drink, brush their teeth, chew gum, or suck on hard candy, cough drops, etc., for 30 minutes following each use of the oral rinse. Subjects who use allowed non-study oral rinse(s) (i.e., Gelclair®, saline solutions) during the study period should ensure that the study oral rinse is used at least 60 minutes after use of a non-study oral rinse and that a non-study oral rinse is not used until at least 60 minutes after use of the study rinse.

Note: Although chemoradiation is complete (i.e. the end of radiation therapy (ERT) visit has occurred), subjects are to complete the full 7 days of study drug for Week 7.

The treatment phase of the study will include: (1) the period of RT treatment with concomitant chemotherapy and (2) all assessments occurring after the last dose of RT, through and including a Week 4 Post-RT follow-up visit (the EOS visit).

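### Duration of severe OM should not be log-rank tested on a cumulative-Gy scale: dose stops accruing at the last fraction, so a later onset can pass for a shorter episode

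*Combined protocol and SAP*

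**What the plan says.** The Efficacy Analyses section of the synopsis gives two durations, each as a number of days from the first WHO Grade ≥ 3 during radiotherapy. One runs to the first Grade 2 or lower, the other to the last Grade ≥ 3 assessment. Three rules apply to both:

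- Test: "The effect of treatment on the duration of severe OM will be assessed using a log rank statistic".
- Subjects who never have severe OM: "his/her duration will be set to 0".
- Subjects whose severe OM never resolves: "will be censored at the last study visit".

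The paragraph then ends: "Analyses will be done using both a scale of days, and a scale of cumulative radiation dose delivered (Gy".

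Both durations can extend past radiotherapy. Secondary Efficacy Endpoints carries the first one "to the first WHO Grade 2 or lower OM assessment during/after radiation therapy" and words the second in the same way. Under Design and Methodology the treatment phase includes "all assessments occurring after the last dose of RT, through and including a Week 4 Post-RT follow-up visit (the EOS visit", and subjects at Grade 2 or above one week after radiotherapy "will return to the clinic at weekly intervals until mucositis resolves". The planned dose varies between subjects: a "minimum cumulative dose of 55 Gray (Gy) and maximum cumulative dose of 72 Gy over approximately 7 weeks".

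The synopsis leaves full statistical detail to a separate SAP. The text under review contains no rule for converting time after the last fraction into Gy.

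**The concern.** Cumulative dose works as a clock only while dose is being delivered. Between the last fraction and the Week 4 visit it stands still, although this is a period in which both durations may end. The only censoring rule covers subjects unresolved at the last visit. Read as written, a subject who heals after radiotherapy is therefore an event at a Gy value fixed on the day of the last fraction.

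For these subjects the value depends on when the episode began and not on how long it lasted. Delaying onset is a secondary objective in its own right and is already tested on both scales. If the rinse delays onset and does nothing else, the Gy duration test can report that delay again under the separate objective of reducing duration. Readers would then count two benefits where there is one. Conversely, faster healing after radiotherapy leaves the Gy value unchanged.

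**Working it through.** **Plan's own figures.** The plan gives no figure for duration. Its one design figure, 23-30 per group, reproduces: the two-proportion formula with continuity correction, 80% power and an assumed one-sided 5% level gives 23 for 75% v 35% and 30 for 75% v 40%. Nothing here depends on it.

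**Inputs.** Fractions of 2.0-2.2 Gy (inclusion criterion 4), typically 35 fractions (Patient Eligibility), total dose 55-72 Gy, and follow-up to 4 weeks after radiotherapy. I assume 2 Gy on five consecutive days of each 7-day week, starting on day 1.

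**Formula.** With w = floor((d − 1)/7), the cumulative dose on day d is C(d) = 2 × [5w + min(d − 7w, 5)], capped at the total T. So C(22) = 2 × 16 = 32 Gy, C(29) = 2 × 21 = 42 Gy, C(43) = 2 × 31 = 62 Gy and C(47) = 2 × 35 = 70 Gy, the last fraction. The Gy duration is C(end) − C(onset). If the episode ends on or after the last fraction, this is T − C(onset).

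**Examples (T = 70 Gy).**

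| Onset | Resolved | Days | Gy |
|---|---|---|---|
| day 22 | day 54 | 32 | 70 − 32 = 38 |
| day 43 | day 75 | 32 | 70 − 62 = 8 |
| day 43 | day 54 | 11 | 70 − 62 = 8 |

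For a subject still severe at the last fraction with or without the delay, onset one week later removes 5 × 2 = 10 Gy, whatever the healing time. The ceiling also moves with the plan. Onset on day 29, still severe at the last fraction, gives 56 − 42 = 14, 70 − 42 = 28 or 72 − 42 = 30 Gy under 56, 70 and 72 Gy plans.

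**Simulation, first duration definition.** The settings were:

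- 30 per arm, 75% incidence in both arms unless stated, zeros included.
- Onset uniform on days 15-36 or 15-40; gamma episodes with median 14, 21 or 28 days.
- Twice-weekly assessment during radiotherapy, then weekly to day 75, with unresolved episodes censored at day 75.
- Two-sided log rank at 0.05, 1,500 trials per scenario (Monte Carlo SE at most √(0.25/1500) ≈ 1.3 points).

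| Scenario | Gy scale rejects | Days scale rejects |
|---|---|---|
| No effect | 5-6% | 5-6% |
| Onset delayed 7 days, nothing else | 27-33% | 6% |
| Healing time after radiotherapy halved | 5-11% | 8-25% |
| Whole duration halved | 48-62% | 72-75% |
| Incidence 75% v 37.5%, nothing else | 46-52% | 47-49% |

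Under these assumptions, 37-74% of severe episodes had their first Grade ≤ 2 assessment after the last fraction. The bottom row comes from the zero rule, which affects both scales and is a separate matter.

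**Other assumptions.** A second simulation took 22 severe cases per arm, no zeros, and onset at mean day 24 (SD 6). With a 7-day delay the Gy test rejected in 24% (median episode 14 days) and 59% (28 days) of runs. With a 14-day delay it rejected in 93% and 98.5%. Nearly all rejections favoured the delayed arm. Across all its scenarios the days test stayed at 4.4-6.9%.

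**Second duration definition.** A 7-day delay gave 16-23% on Gy and about 6% on days.

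**The case against.** The strongest counter-argument is that the fault lies in the event rule and not in the Gy scale. If subjects still severe at the last fraction were censored there, rejection under pure delay would return to about nominal (2.4-7.3% across the settings tried), and one sentence would save the test. That is true. However, the synopsis does not state this rule, and it would discard the healing after radiotherapy that both endpoints expressly include. The separate SAP may contain a convention, so what would actually be run is uncertain. The criticism applies to the synopsis read literally.

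Four further points stand in part:

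- The size of the effect rests on assumed onset and episode-length distributions. The direction does not.
- The 27-33% assumes equal incidence, whereas the plan expects 75% v 35-40%. Adding the delay to that difference gave Gy 81-87% against days 43-51%, so the gap remains.
- Planned dose is fixed before randomisation, so the moving ceiling adds noise, not expected bias.
- Gy delivered while severe during radiotherapy has a meaning, but for a single episode still severe at the last fraction it is the same T − C(onset). It should be described as exposure and not tested as duration.

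**Conclusion.** The concern holds. That the Gy value equals total dose minus onset dose once dosing ends is arithmetic and needs no assumption beyond the literal reading of the event and censoring rules. Episodes that resolve before the last fraction are not affected. How many subjects are affected, and by how much, depends on distributions the documents do not give.

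Under the assumptions shown, a pure 7-day delay is reported as a duration effect in roughly a quarter to a third of trials under the first definition with zeros included. Without zeros and with long episodes the figure is up to 59%. The second definition gives about a sixth to a quarter. The days test stays near 5%. For a real halving of duration, the Gy test is weaker than the days test already planned.

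This is a should-fix. The analyses are secondary, and the primary endpoint, Fisher test, sample size and days analysis do not change.

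**What to change.** In the duration paragraph of Efficacy Analyses, replace the sentence on two scales with a statement that both durations are analysed in days only. Keep the Gy scale for time to onset and for incidence by cumulative IMRT, where the dose clock is meaningful. If a Gy summary of severe OM is wanted, define it as Gy delivered while at Grade ≥ 3 during radiotherapy, label it as exposure, and report it descriptively without a log-rank test. Bring any Gy convention in the separate SAP into line with this wording.

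The cost is wording in the synopsis and SAP. Two log-rank tests are dropped, one per duration definition, and no new data are needed. The change does not resolve the effect of setting unaffected subjects to zero, which needs its own decision.
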